Increasing the winter community participation of older adult wheelchair users

NCT02622828

Increasing the winter community participation of older adult wheelchair users

Participation has been defined by the World Health Organization as “involvement in a life situation” and includes involvement in community, social, and civic realms.¹ The concept of participation is more complex than simply considering the extent to one does or does not engage in a prescribed activity, rather it also has qualitative attributes that relate to the nature and self-perceived meaning of participation.² Research has supported the association between community participation among people with disabilities, and outcomes such as higher subjective ratings of quality of life and independence, improved sense of belonging, and positive self-perception of health.³⁻⁵

In Canada, 1.2 million people use mobility aids, such as wheelchairs, as a means to participate and engage in meaningful occupations within their community.⁶ Furthermore, the prevalence of mobility issues reported increases as people age, with approximately one-quarter of Manitobans age 75 or over reporting mobility issues.⁷ However, users of wheeled mobility devices (WMD) face numerous environmental barriers to community participation including barriers such as limited access to accessible public transportation,⁸ lack of or poorly maintained ramps,⁸⁻¹¹ lack of accessible parking,⁸ negative societal attitudes,⁸ and lack of enforcement of accessibility regulations.¹²

One environmental barrier that WMD users in Manitoba acutely experience is winter weather. In a web-based survey of 99 Manitoban WMD users,¹³ 80% of respondents reported needing additional help for home maintenance, transportation, and community access in the winter; however 57% reported not receiving that needed help. Respondents reported that limited community participation in winter led to feelings of loneliness, isolation, fear, and anxiety. Forty-two percent of respondents reported reducing their community participation frequency from almost daily in summer, to once or twice a week (or less) in winter; this finding was associated with older adult WMD users and those who lack access to family/friends for transportation. These results are particularly concerning, given a recent systematic review of community-dwelling older adults that provides strong evidence to support the positive impact of involvement in social, recreational, spiritual, and physical activity on health and quality of life.¹⁴

Though we are beginning to gain an understanding of participation barriers specific to WMD users in the winter, few studies have sought to address these barriers through the development of new technology or adapting environmental features.¹⁵⁻¹⁷ The five environmental domains identified by International Classification of Functioning, Health and Disability (ICF)¹⁸ (i.e., technological, natural, physical, social/attitudinal, and policy) interact with a person with a health condition to either promote or limit activity and participation. Targeted interventions directed toward one or more of those domains may be an effective way of addressing reduced winter community participation. The purpose of this study is *to examine whether intervention strategies targeted at the level of the environment can successfully promote the community participation experiences of community-dwelling older adult Manitobans who use WMD in the winter.* The findings of this pilot study will help determine the feasibility of, and guide the development of, a proposal targeted at conducting a larger scale study.

Method

Overview Using a single-subject design, five older adult WMD users will each select three community-based participation goals to work on throughout the winter months. Each participant will work with an occupational therapist to receive individually-focused interventions aimed at increasing community participation. A client-centred outcome measure will be used to set initial goals, and to measure change in performance and satisfaction with performance.

Detailed Description Given the subjective nature of participation the experience of participating, community-based interventions should consider the individual nature of participation occupations and strive to engage individuals in occupations considered meaningful to them.¹⁴ This study will use an Interrupted Time Series Design (ITS), a quasi-experimental single-subject design suitable for evaluating the effectiveness of individually-designed interventions.¹⁹ Using ITS, each participant serves as his/her

own control, multiple baseline measurements are taken, and multiple measures of the targeted outcome are collected throughout the study trajectory.²⁰

Participants

This application is a pilot study, and thus feasibility of the research approach will be examined by recruiting five older adult Manitobans who are wheelchair users. Participants will be recruited through collaboration with one or more of the five Winnipeg Regional Health Authority ACCESS Centres and other health resource centres for seniors including Active Living Coalition for Older Adults (ALCOA), Age and Opportunity, Creative Retirement Manitoba, Healthy Aging Resource Team (HART) and the Independent Living Resource Centre (ILRC). Posters will be used to recruit participants. Participants will be screened for inclusion by the occupational therapist using the Geriatric Depression Scale-Short Form²¹ (GDS-SF) and the Montreal Cognitive Assessment²² (MOCA). Inclusion criteria include: age 70 or older, user of a manual or power wheelchair or scooter for outdoor mobility, self-identifies a reduction in community participation throughout the winter months, community-dwelling, GDS-SF score of 5 or less, MOCA score >26, and lives within the perimeter of Winnipeg. If the score on the GDS-SF is >5 (indicating mild depression), the individual will not be included in the study and with permission of the individual, the occupational therapist will telephone the individual's physician and suggest further assessment.

Measures

The **Canadian Occupational Performance Measure**²³ (COPM) is a client-centered outcome measure designed to detect changes in performance and satisfaction in occupations that the individual has self-identified as being important and difficult to perform. The COPM has well-established psychometric properties and will be used as the primary outcome measure and will be used to set treatment goals, determine baseline stability, and detect change in performance of, and satisfaction with, the goals.

The **Activity Card Sort**²⁴ (ACS) uses a Q-sort methodology where photographs of people performing various activities are sorted into categories that the participant indicates interest in performing. The ACS will be used to identify valued instrumental, leisure and social activities that the person has performed in the past and/or desires to participate in in the future and will guide the formation of goals on the COPM. The **WHO-DAS 2.0**²⁵ is a generic self-report health status measure, linked to the concepts of health and disability outlined in the ICF and intended to identify limitations in six domains, including self-care, and community and social functioning experienced over the past 30 days. The WHO-DAS 2.0 is responsive to change, has excellent internal consistency, established content validity, and high convergent validity. The WHO-DAS 2.0 will be used to identify changes in overall health status that occur through the study. Follow-up **semi-structured interviews** will be conducted at the end of the intervention phase, to gain the perspective of each participant of the experience and personal value of working to increase winter community participation. Interview questions will address barriers and supports to participating in self-identified occupations and impact on sense of inclusion and engagement in the community.

Procedure (repeated for each of 5 participants, entered concurrently into study)

Recruit/screen for inclusion ACS; COPM goal-setting phase WHO-DAS 2.0	Week 0	Occupational therapist will conduct initial assessment to establish goals using the ACS and COPM.
COPM baseline measurements (2x/week)	Weeks 1-4	Minimum 24 data points required to conduct statistical analysis ¹⁹
Intervention related to goal 1 (e.g. attend weekly spiritual services at local place of worship) Continue with baseline measurements (2x/week) for goals 2 and 3	Weeks 5-7	A sample intervention for goal 3 might include working with participant to: identify appropriate neighborhood grocery store suitable for mobility/accessibility needs (e.g.

Intervention for goal 2 (e.g. participate in wheelchair yoga class 1x/week) Continue with baseline measurements (2x/week) for goal 3	Weeks 8-10	store that has scooter and basket available for customer use), determine regular transportation means and travel route, prepare weekly grocery list, learn to use debit card to pay for groceries.
Intervention for goal 3 (e.g. weekly grocery shopping at local grocery store)	Weeks 11-13	
Follow up phase (COPM/WHO-DAS) Follow-up interview (week 16 only)	Weeks 16 and week 20	Research assistant conducts follow up interviews and administer follow-up COPM and WHO-DAS 2.0

Analysis

COPM data will be plotted and visually inspected to gain an understanding of the timing and nature of any change. Statistical analysis will be conducted using the celeration line and C statistic¹⁹, where the proportion of data points above and below the line is calculated and compared to a probability table to determine statistical significance. Repeated measures ANOVA will be used to identify change on the six domains of the WHO-DAS 2.0. Guided by an Interpretive Descriptive approach²⁶, qualitative interviews will be transcribed verbatim and directed content analysis²⁷ used to gain a descriptive and interpretive understanding of clinically relevant issues and suggestions for future study.

Importance and Relevance to Aging

Approximately one-third of Manitobans aged 65 or over reported emotional and social loneliness and older adults reported a decline in leisure activity participation with increasing age.⁷ Older adult WMD users in Manitoba bear a disproportionate burden in the winter – when aging, mobility limitations, and weather coincide to create conditions not conducive to community participation. A recent systematic review identified strong evidence to support the use of occupation and client-centred interventions in maintaining instrumental activities of daily living abilities of community-dwelling older adults.²⁸ However, evidence is required to identify whether, and how, we can use individually-focused interventions at the level of the environment to improve or maintain the community participation experiences of community-dwelling older adults who use WMD,²⁸ particularly in the winter.

Qualifications and Strategic New Direction

My program of research focuses on understanding the intersection between assistive technology users and their environments. I primarily use client-centered approaches to inquiry, specifically qualitative methods, photovoice, case study, and mixed methods. While aging has not been a particular focus in past research, findings from a recent survey that I conducted¹³ indicated a disproportionate burden placed on older adults who are WMD users in terms of limitations in community participation in winter. I view this application as an important opportunity to explore innovative ways of addressing those challenges.

Publications and Future Applications

One peer-reviewed publication and a minimum of two professional presentations on this research will result from this study. While the sample size of five will not provide evidence of a treatment effect, the findings can be used to determine sample size required for a larger scale study proposal targeted at the Canadian Institutes of Health Research. This study will form a key component of a larger program of research focused on improving winter community participation among people with disabilities.

Timeline

Hire research assistant and OT; Submit HREB	July –August 2015
Recruit/Baseline phase	November – December 2015
Intervention (to occur over mid-winter)	January - March 2016
Follow up	Complete by April 2016

Data analysis	Complete by July 2016
Presentations/publications	May –September 2016

References

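### As listed, the Procedure table schedules no COPM rating of a goal from the start of its intervention until week 16

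*Combined protocol and SAP*

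**What the plan says.** Under Method, Detailed Description, the design is an interrupted time series in which each participant is his or her own control and "multiple measures of the targeted outcome are collected throughout the study trajectory".

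The Procedure table sets out the COPM ratings:

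- Weeks 1-4: baseline ratings twice a week, with the note "Minimum 24 data points required to conduct statistical analysis".
- Weeks 5-7, intervention for goal 1: "Continue with baseline measurements (2x/week) for goals 2 and 3".
- Weeks 8-10, intervention for goal 2: "Continue with baseline measurements (2x/week) for goal 3".
- Weeks 11-13: "Intervention for goal 3 (e.g. weekly grocery shopping at local grocery store"; no rating of any goal is listed.
- Weeks 16 and 20: "Follow up phase (COPM/WHO-DAS".

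Measures makes the COPM the primary outcome, used to judge baseline stability and to detect change in the goals. Under Analysis, "COPM data will be plotted and visually inspected to gain an understanding of the timing and nature of any change". The celeration line and C statistic follow, and "the proportion of data points above and below the line is calculated and compared to a probability table". Publications and Future Applications states that five participants will not give evidence of a treatment effect.

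**The concern.** A goal drops off the list of rated goals in the week its intervention begins and returns only at follow-up. If staff work from the table, the part of the series in which change is expected is never recorded, and those ratings cannot be recovered later.

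Three things are then lost. Change during the intervention weeks is unobserved. The staggered starts cannot show when change began: goal 1 could improve in week 5 or in week 15 and the plot would look the same. The celeration-line count rests on two points per goal. As a pilot of the research approach, the study would also not try out the measurement schedule that a larger study would need.

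**Working it through.** **Inputs.** Twice-weekly rating, three goals, and the week ranges, all from the Procedure table. Alpha, sidedness, null proportion and any correlation between ratings are not stated in the plan; values used below are assumptions.

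**1. The plan's own figure.** Weeks 1-4 give 2 × 4 = 8 ratings per goal. Over three goals, 8 × 3 = 24, exactly the stated minimum. The table does not say that this pooled count is the unit meant.

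**2. Ratings as listed.**

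| Goal | Before start | Start to week 15 | Weeks 16 and 20 | Total | Last rating before week 16 | Gap to week 16 |
|---|---|---|---|---|---|---|
| 1 | 2 × 4 = 8 | 0 | 2 | 10 | week 4 | 16 − 4 = 12 weeks |
| 2 | 2 × 7 = 14 | 0 | 2 | 16 | week 7 | 16 − 7 = 9 weeks |
| 3 | 2 × 10 = 20 | 0 | 2 | 22 | week 10 | 16 − 10 = 6 weeks |

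No goal reaches 24 by itself, even with a week 0 rating added (11, 17, 23).

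**3. Celeration-line count as listed.** If each goal is tested separately with a null proportion of 0.5, the smallest one-sided p from two points is 0.5² = 0.25. Pooling a participant's three goals gives six points and 0.5⁶ = 0.0156, so the floor depends on how the test is set up. The C statistic uses the whole series and has no such floor.

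**4. All three goals rated twice a week through week 13.** Each goal has 2 × 13 = 26 ratings, split 8/18, 14/12 and 20/6 before and after its start, plus two follow-ups (28 in all).

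- Contacts in weeks 1-13, with all goals rated at the same contact: 8 + 6 + 6 = 20 now; 20 + 6 = 26 revised.
- Goal-ratings in weeks 1-13: 8 × 3 + 6 × 2 + 6 × 1 = 42 now; 26 × 3 = 78 revised.

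**5. What the tests are worth after the change.** With a 0.5 null and one-sided 0.05, the nominal counts through week 13 are:

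- 13 or more of 18 (p = 0.048)
- 10 or more of 12 (p = 0.019)
- 6 of 6 (p = 0.0156)

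These ignore error in the extrapolated baseline line. In 20,000 simulated series with no change, independent normal ratings and a line through the medians of the two baseline halves, the counts were reached in about 42%, 26% and 9% of runs.

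For the C statistic, C = 1 − Σ(successive differences)² / (2 × SS), where SS is the sum of squares about the mean, with SE = √[(n − 2)/((n − 1)(n + 1))]. With no change and an assumed lag-1 correlation of 0.5 between neighbouring points (follow-ups treated as neighbours too), Z exceeded 1.645 in about 34%, 53% and 68% of runs for 10, 16 and 22 points, and in about 79% for 28 points. With independent ratings the rate was about 5% throughout.

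**The case against.** The best defence is that silence is being read as an instruction to stop. The rows say which goals remain in baseline, and a treated goal's ratings could no longer be called baseline. The Detailed Description promises measurement throughout, and an inspection of timing presupposes ratings during intervention. Read together, continued rating is a coherent intention. This stands, and a reader should not infer that the table ends the rating of treated goals: it does not say so. But no place lists those ratings or gives a frequency, and the readings differ. Rating each goal only in its own three-week block would give 16, 22 and 28 points with follow-up, against 28 for each goal if all are rated through week 13.

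Three stronger inferences are also unsupported:

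- **That the 24-point minimum is wrong or missed.** It is met exactly when pooled over weeks 1-4. It is missed per goal as listed, but the unit is not stated and rests on a cited source not available here.
- **That a treatment effect would be missed.** The plan itself disclaims evidence of an effect with five participants.
- **That more ratings would make the planned tests valid.** The error rates under no change in step 5 say otherwise. Under the assumed correlation, the longer series makes the C statistic's false-positive rate worse.

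The added burden on participants aged 70 or older is a fair point, and twice weekly is one of several frequencies that would reconcile the text.

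**Conclusion.** The concern holds as a mismatch between the table and the rest of the plan, and should be fixed. The count of two post-start ratings per goal and the 12-, 9- and 6-week gaps follow from the table alone, on the condition that it is followed as listed. The 0.25 floor needs the further assumptions of separate tests and a 0.5 null. The simulated rates depend on their stated models and show only that neither test can carry a significance claim here. The loss is an observed intervention phase for the primary outcome and a proper trial of the measurement schedule. Confidence is medium because continued rating may have been intended. The unit of the 24-point minimum is a minor clarification.

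**What to change.** Reconcile the Procedure table with the Detailed Description: in the rows for weeks 5-7, 8-10 and 11-13, state that the COPM is rated twice a week for all three goals, and keep the week 16 and 20 follow-ups.

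The cost is six further rating contacts per participant, all in weeks 11-13, or 30 over five participants. Of the 36 additional goal-ratings each, 18 fall at contacts that already occur in weeks 5-10 and 18 at the new ones. Goal 3 would still have only six ratings between its start and follow-up.

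In Analysis, state that the celeration-line and C-statistic results are descriptive and are read beside the plot. In the weeks 1-4 row, state the unit of the 24-point minimum after checking the cited source; the revised schedule meets 24 whether counted per goal or pooled over goals.

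### Repeated measures ANOVA on three WHO-DAS readings in five people, with no rule for a missed visit, would in its usual form discard a usable week 0 to 16 change when only week 20 is missed

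*Combined protocol and SAP*

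**What the plan says.** The combined protocol and SAP gives WHO-DAS 2.0 a distinct job in Measures: "The WHO-DAS 2.0 will be used to identify changes in overall health status that occur through the study". The Procedure table places the first reading at week 0 ("Recruit/screen for inclusion ACS; COPM goal-setting phase WHO-DAS 2.0"). The other two come in the follow-up phase ("Follow up phase (COPM/WHO-DAS) Follow-up interview (week 16 only"), timed at "Weeks 16 and week 20". That makes three readings per person.

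The Analysis section gives the method in one sentence: "Repeated measures ANOVA will be used to identify change on the six domains of the WHO-DAS 2.0". It does not say which variant of ANOVA is meant. Nothing in the document covers missed visits, withdrawal, replacement, imputation or an expected dropout rate.

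Two statements set the weight of the point. COPM "will be used as the primary outcome measure", so WHO-DAS is not primary. Publications and Future Applications says: "While the sample size of five will not provide evidence of a treatment effect, the findings can be used to determine sample size required".

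**The concern.** In its usual form, repeated measures ANOVA analyses only participants with a complete set of readings. A person seen at weeks 0 and 16 but not at week 20 would contribute nothing, although the change across the intervention period was observed. With five people, one such loss removes a fifth of the sample.

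The participants are aged 70 or over and use a wheelchair or scooter outdoors, so a missed late visit is plausible. The calendar is also tight. The Timeline starts intervention in January 2016 and finishes follow-up by April 2016. Week 20 ends 16 weeks (112 days) after week 5 begins, so it passes 30 April if week 5 starts after about 9 January. This does not show that anyone would miss week 20.

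Two things are at stake. One is the precision of a health-status result that could feed the planning of a larger study. The other is possible bias, if those who miss visits differ in health from those who attend.

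**Working it through.** The plan has no figure to reproduce: it gives no significance level, SD, effect size, dropout rate or calculation behind the five participants.

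**Inputs from the document.** n = 5 (Participants: "feasibility of the research approach will be examined by recruiting five older adult Manitobans who are wheelchair users"); three readings per person (Procedure table); repeated measures ANOVA for each domain (Analysis).

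**Assumptions.** 95% confidence; equal variances and sphericity, so that residual error is pooled across weeks; participant treated as a block (fixed participant effects) for the available-data model; the same SD of change in both analyses.

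**Step 1: readings used and error degrees of freedom.** Error df = readings − 1 − (participants − 1) − (weeks − 1).

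- No loss: 15 − 1 − 4 − 2 = 8.
- One person misses week 20 (14 readings collected). Complete-case: 12 readings from 4 people, 12 − 1 − 3 − 2 = 6. Available-data: 14 − 1 − 4 − 2 = 7.
- Two people miss week 20 (13 collected). Complete-case: 9 readings from 3 people, 9 − 1 − 2 − 2 = 4. Available-data: 13 − 1 − 4 − 2 = 6.

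**Step 2: half-width for the week 0 to 16 change.** Everyone in these scenarios has weeks 0 and 16, so the estimate is the mean of the within-person differences. Its variance is 2σ²/n, where σ² is the residual variance and n the number of people analysed. The SD of change is √2·σ, so the half-width in SD of change is t(0.975, error df)/√n.

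| Scenario | Complete-case ANOVA | Available-data model | Ratio |
|---|---|---|---|
| No loss | 2.306/√5 = 1.03 | 1.03 | 1.00 |
| One missed week 20 | 2.447/√4 = 1.22 | 2.365/√5 = 1.06 | 1.16 |
| Two missed week 20 | 2.776/√3 = 1.60 | 2.447/√5 = 1.09 | 1.46 |

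**Step 3: where the gain stops.** If one person misses both follow-ups, 13 readings are collected and the complete-case analysis uses 12, with error df 6. The available-data model has 13 − 1 − 4 − 2 = 6. The extra reading is a lone baseline and adds no within-person information on change.

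**Step 4: direction of any selection.** Dropout at week 20 was simulated under assumed values: 1,000,000 subjects, between-person SD 1, within-person SD 0.6, logistic dropout, higher score = worse health. The mean baseline of completers was 0.00 when dropout was unrelated to health, −0.24 when worse baseline drove it, −0.18 when worse week 16 health drove it, and +0.18 when better week 16 health drove it. The sign follows the mechanism assumed, and the document gives none.

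**The case against.** The best defence is that the plan nowhere says incomplete participants are deleted. The term repeated measures ANOVA does not exclude a fit to all available readings. WHO-DAS is secondary, the protocol disclaims evidence of effect, and with five people a listing of individual trajectories may serve as well as any model. Most of this stands. Deletion is the method's usual behaviour and not a written rule, and the consequence is small. But the plan names a method whose common form deletes people and has no rule to prevent it, so the gap is real.

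A reader might infer more than the document supports:

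- **That the analysis will select healthier completers.** No dropout rate, reason or mechanism is given, and step 4 shows the selection can be nil or reversed.
- **That one loss widens the interval by 28% and two double it.** Those ratios come from paired-t intervals on the week 0 to 16 differences alone (2.776/√5 = 1.24; 3.182/√4 = 1.59; 4.303/√3 = 2.48). The planned ANOVA and the mixed model both pool error across weeks, which gives about 16% and 46%.
- **That the chance of this loss is 41% or 67%.** With assumed rates of 10% or 20% per person, 1 − 0.9⁵ = 0.41 and 1 − 0.8⁵ = 0.67 are the chances that at least one person misses any follow-up. The loss in step 2 needs week 16 attended and week 20 missed, which is a narrower event.
- **That someone who stops working on a goal leaves follow-up.** The schedule is set for all five participants, and weeks 16 and 20 are not made conditional on finishing the goals.
- **That a mixed model removes the bias.** It helps where observed readings explain the missed visit. If unobserved decline after the last reading causes it, the mixed model is biased too.

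**Conclusion.** The point holds as a low-severity improvement. The plan has no rule for a missed WHO-DAS reading, and the usual form of its named method would discard an observed week 0 to 16 change when only week 20 is missed. The cost in precision is an interval about 16% wider for one such loss and about 46% wider for two, assuming equal variances, sphericity and the same SD of change. With complete data there is no cost. Bias is possible if dropout relates to health, but its direction and size cannot be stated from this document. The primary COPM analysis is unaffected.

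**What to change.** In Analysis, replace the WHO-DAS sentence with a linear mixed model for each domain: random participant intercept, week as a factor, small-sample degrees of freedom, all available readings used. Report the week 0 to 16 and week 0 to 20 changes separately, plot each participant's trajectory, and list reasons for missed visits. In Procedure, add a sentence that the scheduled week 16 and 20 assessments are sought from everyone who has not withdrawn consent.

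The cost is a change of wording, with no added visits. With complete data and a non-negative between-person variance estimate, the model gives the same test of time as the standard ANOVA.

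The limits should be stated alongside. The model is fragile with five people, so the individual plots should carry much of the interpretation. It adds nothing on change when both follow-ups are missed, and it does not correct for visits missed because of unobserved decline.

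### Does the plan promise more than five participants can deliver when it says the findings can set the sample size of a larger study?

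*Combined protocol and SAP*

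**What the plan says.** The introduction frames the work as feasibility: "The findings of this pilot study will help determine the feasibility of, and guide the development of, a proposal". The Participants section ties the number enrolled to the same aim, by "recruiting five older adult Manitobans who are wheelchair users". No power calculation is offered for the five, and none would be expected.

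The Measures section says the COPM "will be used as the primary outcome measure". In the Analysis section, COPM data are plotted and inspected, then tested with the celeration line and the C statistic; in the plan's description, "the proportion of data points above and below the line is calculated and compared to a probability table". The only group-level model is for another instrument: "Repeated measures ANOVA will be used to identify change on the six domains of the WHO-DAS 2.0". The Procedure table schedules COPM scores twice weekly in baseline, and both COPM and WHO-DAS 2.0 at weeks 16 and 20.

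Publications and Future Applications first concedes that "the sample size of five will not provide evidence of a treatment effect", then adds that "the findings can be used to determine sample size required for a larger scale study proposal". The document does not state the larger study's design, outcome, target difference, significance level or power.

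**The concern.** A stated use of the pilot seems to have no matching output. Since the plan disclaims evidence of an effect, variability is the natural quantity the pilot could pass on. Yet none of the COPM analyses yields a between-participant SD. The C statistic uses variability within a series, which is a different quantity. The WHO-DAS 2.0 model does estimate variances, but not for the primary outcome, and no domain is named as a basis for sizing.

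Even if an SD were calculated, five people give it only 4 degrees of freedom (df). Read literally, the claim to determine a sample size would let a funding proposal rest on a very unstable figure, and the larger study could be badly under- or over-sized. That risk falls on the later study, not on this one.

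**Working it through.** **Plan's own figure.** There is nothing to reproduce. The five is a feasibility number, and no SD, effect, significance level or power is stated for the larger study.

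**Assumptions (none from the plan).** One roughly normal summary per participant, five completers, a later comparison of means, a fixed target difference, the observed SD used as it stands, and no external data. For the power figures and the illustration: two-sided 5% level and 80% nominal power (z values 1.96 and 0.842).

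**Span of the required number.** With n = 5, df = 5 − 1 = 4. The required N is proportional to SD², so its 95% limits, as multiples of the calculated N, are df/χ²(0.975) and df/χ²(0.025).

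- Lower: 4/11.143 = 0.359
- Upper: 4/0.4844 = 8.257
- Ratio: 11.143/0.4844 = 23.0
- For the SD itself: √0.359 = 0.60 and √8.257 = 2.87 times the observed SD

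On the same 4 df the span is 13.3-fold at 90% confidence and 7.3-fold at 80%. The ratio does not depend on significance level, power, allocation or target difference, provided these are held fixed.

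**Illustration (assumed difference 2, assumed SD 2, two equal arms).** n per arm = 2 × (1.96 + 0.842)² × 2²/2² = 15.7, so 16. At the limits: 15.7 × 0.359 = 5.6, so 6; and 15.7 × 8.257 = 129.6, so 130.

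**True power if the SD were plugged in.** Power = Φ(2.802 × √(χ²₄/4) − 1.96). Averaged over the chi-square distribution, this gives 0.680. Power falls below 0.5 when χ²₄ < 4 × (1.96/2.802)² = 1.96, which has probability 0.256.

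**WHO-DAS 2.0 model.** Five people at weeks 0, 16 and 20 give (5 − 1) × (3 − 1) = 8 error df under sphericity. The limits are 0.456 and 3.670, an 8.0-fold span.

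**What this shows.** The arithmetic is right, but it describes any SD estimated from five values. It does not test anything the plan states, because the plan never says that such an SD will be used alone. If the larger study kept the single-subject design, within-series variability would matter as well, and these figures would not be the main consideration.

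**Would a pre-stated COPM summary help?** The COPM data it needs are already scheduled. But pre-intervention scoring runs over weeks 1–4 for goal 1, weeks 1–7 for goal 2 and weeks 1–10 for goal 3. The intervention blocks end at weeks 7, 10 and 13, so week 16 falls 9, 6 and 3 weeks afterwards. A single averaged change score would mix different baselines and lags. By the Timeline it would also span a season, from a November–December baseline to follow-up complete by April. The SD of that uncontrolled change need not be the SD a controlled study requires, and its 95% interval would still be 0.60 to 2.87 times the estimate.

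**The case for a change.** The best case for a change is that it is cheap. One softer verb would bring the sentence into line with the feasibility aim, and a few added sentences would commit the team to reporting an SD with its interval. No visits or participants would be added. Pre-stating the goals, visit and scale would prevent a convenient choice later, and reporting the interval would show how little five people can say. One dropout would make matters worse: with 3 df the span is 43-fold.

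Some of this stands. The verb is stronger than the design supports, and the Analysis section names no between-participant COPM summary. But the sentence says only that the findings can be used this way, and the findings are not confined to the listed tests: the repeated scores themselves will be in hand. The summary is also harder to define than it appears, given the staggered baselines, and once defined it would carry little planning information. Which variance is needed, and how to allow for its uncertainty, depends on a design not yet chosen. Those decisions belong in the later proposal.

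**Conclusion.** No change is needed. The plan does not derive a between-participant COPM SD, and an SD on 4 df would be a poor sole basis for sizing a study: 0.36 to 8.3 times the calculated number at 95%, with mean true power about 68%. Those figures hold only under a group-mean design with the pilot SD used unaided, a route the document nowhere adopts. What remains is a loosely worded, permissive sentence about future use and a descriptive summary that a competent analyst can produce from scheduled data when the later proposal is written. No result, test or conclusion of this pilot depends on it.
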